5.1.4 Safety Endpoints

Serious Adverse Event (SAE)

An event categorized as "Adverse Event" with the indicator flag "Serious" equal to "Yes" on the Events eCRF starting on or after signing of the informed consent and up to the End of Study date.

Treatment-emergent Adverse Event (TEAE)

An event categorized as "Adverse Event" on the Events eCRF starting on or after first dose of investigational product, as determined by "Did event start before first dose of investigational product" equal to "No" or missing, and up to the End of Study date.

Serious TEAE

A TEAE with the indicator flag "Serious" equal to "Yes" on the Events eCRF.

Treatment-emergent Adverse Device Effect

A TEAE with the indicator flag "Is there a reasonable possibility that the event may have been caused by the investigational device" equal to "Yes" on the Events eCRF.

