8.2.4 Adverse Events and Serious Adverse Events

8.2.4.1 Time Period and Frequency for Collecting and Reporting Safety Event Information

8.2.4.1.1 Adverse Events

The adverse event grading scale to be used for this study will be the Common Terminology Criteria for Adverse Events (CTCAE) and is described in Section 11.4.

The investigator is responsible for ensuring that all adverse events observed by the investigator or reported by the subject that occur after first dose of investigational product through the end of study are reported using the Event CRF.

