8.2.4.1.2 Serious Adverse Events

The investigator is responsible for ensuring that all serious adverse events observed by the investigator or reported by the subject that occur after signing of the informed consent through end of study are reported using the Event CRF.

All serious adverse events will be collected, recorded and reported to the sponsor or designee within 24 hours of the investigator's knowledge of the event, as indicated in Section 11.4. The investigator will submit any updated serious adverse event data to the sponsor within 24 hours of it being available.

The criteria for grade 4 in the CTCAE grading scale differs from the regulatory criteria for serious adverse events. The investigator is to determine whether these grade 4 abnormalities are serious adverse events based on the definition of serious adverse events as per Appendix 4 (Section 11.4).

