9.6.2 Adverse Events

The Medical Dictionary for Regulatory Activities (MedDRA) version 23.0 or later will be used to code all adverse events (AEs) to a system organ class (SOC) and a preferred term (PT). All AEs will be graded using the Common Terminology Criteria for Adverse Events (CTCAE) Version 4.03. All AE summary tables described below will be summarized by treatment group using subject incidence.

The subject incidence of AEs will be summarized for all treatment-emergent adverse events (TEAEs), serious AEs, AEs leading to withdrawal of investigational product, fatal AEs, and adverse events of interest (EOI) including

- Ischaemic Central Nervous System Vascular Conditions SMQ (Narrow)
- Ischaemic Heart Disease SMQ (Narrow and Broad)
- Peripheral Arterial Disease AMQ (Narrow)
- Hypertension SMQ (Narrow and Broad)
- Constipation AMQ (Narrow and Broad)
- Alopecias AMQ (Narrow and Broad)
- COVID-19 SMQ (Narrow)

Subject incidence of all TEAEs, SAEs, AEs leading to withdrawal of investigational product, fatal AEs, and device related AEs will be tabulated by SOC in alphabetical order and PT in descending order of frequency **based on the AMG 334 140 mg dose, then Placebo dose and then alphabetically**.

Subject incidence of EOI (standardized MedDRA queries [SMQ] and/or Amgen medical queries [AMQ]) will also be summarized according to their categories and PT in descending order of frequency.

In addition, summarizes of all TEAEs and SAEs occurring in at least 3% of the subjects by PT in any treatment arm will be provided in descending order of frequency **based on**

the AMG 334 140 mg dose, then Placebo dose and then alphabetically. Summaries of all TEAEs and SAEs will be tabulated by SOC, PT, and grade.

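### By-arm SAE tables count from informed consent, so serious events before the first dose fall under erenumab or placebo, and the SAP's own Serious TEAE is used in no table

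*SAP*

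**What the plan says.** SAP 5.1.4 gives three relevant definitions.

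- An SAE is a serious adverse event on the "Events eCRF starting on or after signing of the informed consent and up to the End of Study date".
- A TEAE is an adverse event "starting on or after first dose of investigational product, as determined by" an Events eCRF question on whether the event began before the first dose. An answer of no, or a missing answer, makes the event treatment-emergent.
- A Serious TEAE is "A TEAE with the indicator flag 'Serious' equal to 'Yes' on the Events eCRF".

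SAP 9.6.2 sets the display: "All AE summary tables described below will be summarized by treatment group using subject incidence". The SOC and PT tables are specified as "Subject incidence of all TEAEs, SAEs, AEs leading to withdrawal of investigational product, fatal AEs, and device related AEs will be tabulated by SOC". The frequency-cut tables are "summarizes of all TEAEs and SAEs occurring in at least 3% of the subjects by PT in any treatment arm", and a further set is broken down by grade. Each of these uses serious AEs or SAEs. Serious TEAE does not appear in 9.6.2, or anywhere else in the SAP after its definition.

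The protocol puts pre-dose serious events in the database. Under Protocol 8.2.4.1.2, SAEs that "occur after signing of the informed consent through end of study are reported using the Event CRF". Under Protocol 8.2.4.1.1, other adverse events are recorded only if they "occur after first dose of investigational product through the end of study are reported using the Event CRF". The Schedule of Activities marks SAE collection in initial screening, run-in and baseline.

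**The concern.** A table by treatment group is read as a table of what happened on that treatment. Here the SAE columns would also hold events from before any study drug was given, for subjects who later entered the safety analysis set. Nothing in SAP 9.6 removes those events or shows them apart.

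The TEAE and SAE tables would also rest on different time bases. A serious event during baseline would appear in the SAE table with no matching entry in the TEAE table beside it. The tables for adverse events of interest carry no stated treatment-emergent limit either, so a serious pre-dose event in one of those categories could enter them. Non-serious events could not, since they are collected only after the first dose.

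SAP 9.6.1 plans no statistical testing of safety data, so these descriptive incidences are the planned by-arm safety evidence. Where SAEs are few, one event placed under the wrong heading is visible.

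**Working it through.** **Which events reach an arm table.** An SAE counts from consent (SAP 5.1.4). The safety analysis set is randomised subjects with at least one dose (SAP 6.4). Pre-dose SAEs of screen failures therefore drop out. Pre-dose SAEs of subjects later dosed stay in.

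**Length of the windows.**

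- Protocol 8.1.1: initial screening up to 3 weeks, run-in 2 weeks, baseline 4 weeks; 3 + 2 + 4 = 9 weeks, or 63 days.
- Treatment period: 16 weeks, or 112 days. The total is 9 + 16 = 25 weeks, which reproduces the duration in Protocol 4.4.2.
- Lower end, with no time spent in initial screening: 14 + 28 = 42 days.

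Pre-dose share of SAE counting time = pre-dose days / (pre-dose days + 112):

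- 42 / 154 = 27%
- 63 / 175 = 36%

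If all three sub-period maxima in Protocol 8.1.1 to 8.1.3 were used together (21 + 18 + 35 = 74 days, beyond the stated 9 weeks), the share would be 74 / 186 = 40%.

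These are shares of time. They become shares of events only if the SAE rate is constant and a screening SAE does not affect whether the subject is randomised.

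**Effect on the tables: an illustration.** The documents give no SAE rates. Assume post-dose risks of 1% on placebo and 2% on erenumab, a pre-dose rate equal to the placebo rate, 288 dosed subjects per arm, and no loss at screening because of an SAE. Pre-dose risk = 1% x pre-dose days / 112, added to both arms.

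| Pre-dose window | Added risk per arm | Placebo | Erenumab | Difference | Ratio |
|---|---|---|---|---|---|
| None (Serious TEAE) | 0 | 1% (2.9 subjects) | 2% (5.8) | 2.9 | 2.00 |
| 42 days | 0.375% | 1.375% (4.0) | 2.375% (6.8) | 2.9 | 1.73 |
| 63 days | 0.5625% | 1.5625% (4.5) | 2.5625% (7.4) | 2.9 | 1.64 |

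Simple addition ignores subjects with both a pre-dose and a post-dose SAE, who count once. If the two are independent, the difference is multiplied by (1 - pre-dose risk): 2.88 x (1 - 0.005625) = 2.86 subjects, which is negligible.

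Over an assumed 16-week placebo risk of 1% to 3%, the added subjects per arm are 288 x 0.375% = 1.1 to 288 x 1.125% = 3.2 for 42 days, and 288 x 0.5625% = 1.6 to 288 x 1.6875% = 4.9 for 63 days. These are upper-end figures, because they make no allowance for screening.

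**The case against.** **The treatment-emergent restriction may have been intended.** The only incidence formula in the SAP (5.6) is headed as the subject incidence of TEAEs. SAP 9.6.2 also uses shorthand elsewhere: it writes device-related AEs where 5.1.4 defines a treatment-emergent adverse device effect. Serious TEAE sits among the safety endpoints, which suggests that it was meant to be reported. This has some force as evidence of intent. However, the text of the formula speaks of a given event during the study, and a heading does not override an explicit SAE definition that starts at consent. Two programmers could build different tables from this text.

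**The SAP follows the protocol.** Protocol 9.4.2.3.1 also lists tables of serious adverse events without a treatment-emergent limit. True, but it sets no time window for those tables; the SAP definition does. The point stands as a reason to document the change.

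**Collection from consent is right.** Agreed. The issue is attribution to an arm, not collection.

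**Stronger readings that the documents do not support.**

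- A reader might infer that real differences between arms are diluted toward none. Randomisation adds the same expected number of pre-dose events to each arm, so the absolute difference is essentially unchanged. A ratio would shrink, but the SAP plans no ratio for safety.
- A reader might infer that 27% to 36% of tabulated SAEs would be pre-treatment. Those figures describe time. Subjects must still meet every criterion after the event, including the judgement-based exclusion 218 and 80% diary compliance in baseline.
- A reader might picture a pre-dose ischaemic SAE shown under erenumab. The exclusions for triptan contraindications and for other clinically significant conditions make screen failure much more likely.
- A reader might extend the point to the fatal-event table. A subject must be alive at first dose to enter the safety analysis set, so that table is not affected.

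**Conclusion.** The point holds as a specification fault of limited size. Followed literally, the plan counts pre-dose serious events of later-dosed subjects under erenumab or placebo, on a time base that does not match the TEAE tables, while the appropriate defined term goes unused.

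Between 27% and 36% of the SAE counting time lies before the first dose. The number of events affected cannot be estimated from the documents. Under the stated assumptions it is at most a few subjects per arm, and because of screening it is probably much smaller, possibly near zero. The consequence is inflated SAE incidence in both arms plus noise. There is no directional bias, and no efficacy result, error rate or sample size is touched.

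**What to change.** In SAP 9.6.2, replace serious AEs and SAEs with Serious TEAEs in every by-arm serious-event table: overall, by SOC and PT, by PT at 3% or more, and by SOC, PT and grade. State that the tables for adverse events of interest are limited to treatment-emergent events. Report SAEs from consent to first dose in a separate listing, not attributed to an arm. Leave the fatal-event table as it is.

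Record the change in SAP section 10, which currently names only the change to the efficacy analysis sets, because the protocol's table list has no treatment-emergent limit.

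The cost is a wording change, one section 10 entry, one programming filter and one listing. The Events eCRF question that the filter needs already exists, and SAP 5.1.4 already treats a missing answer as treatment-emergent, so an SAE is not lost for lack of an answer. All SAEs remain reported.

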5.2 Study Dates

Informed Consent Date

The date on which subject signs the informed consent form.

Date of Ready for Daily Diary Entry in Baseline

The date on which an eDiary device is ready for daily diary entry after completion of run-in period.

Randomization Date

Randomization Date is defined as the date subject was allocated to a treatment group.

Enrollment Date

Enrollment Date is defined as the randomization date.

First IP Dose Date

First IP Dose Date is the date on which a subject is administered the first dose of IP following randomization as recorded on the IP Administration eCRF. The first IP dose may be the same day or after the randomization date.

Last IP Dose Date

Last IP Dose Date is the date on which a subject is administered the last dose of IP as recorded on the IP Administration eCRF.

End of Study (EOS) Date

End of study (EOS) date is defined as the last date on which the subject participates in the study as recorded on the End of Study eCRF.

5.3 Study Points of Reference

Run-in Assessment

Run-in assessment is designed to determine the entry eligibility for baseline period.

Baseline Assessment

Baseline assessment for the endpoint of the interest is defined as the last non-missing measurement taken or the monthly interval assessed (for endpoints derived from daily eDiary collection during baseline period) before the first dose of investigational product. In cases where baseline measurements are taken on the same day as IP, it will be assumed that these measurements are taken prior to IP being administered. For subjects who are randomized but not dosed after the randomization, the baseline of the study is defined as the last non-missing measurement prior to or on the date of randomization.

Study Day 1

Study Day 1 is defined as the first IP dose date. For subjects who are randomized but not dosed after randomization, the Study Day 1 is defined as the date of randomization.

Study Day

Study Day is defined as the number of days from Study Day 1.

Before Study Day 1:

Study Day = (Date of Interest – Date of Study Day 1)

On or after Study Day 1:

Study Day = (Date of Interest – Date of Study Day 1) + 1

Therefore, the day prior to Study Day 1 is -1.

5.4 Study Time Intervals

5.4.1 Monthly Intervals for Efficacy Endpoints Derived From Daily Diary Collection

The (4-week) monthly intervals for efficacy endpoints derived from daily eDiary collection during baseline and months 1, 2, and 3 will be determined based on each subject's monthly IP dosing dates. When an IP is missed or discontinued, a 28-day monthly interval will be used. Any eDiary data occurring after EOS date will not be included in the analysis.

Applicable efficacy endpoints utilizing the monthly intervals in Table 5-1 include:

• Monthly migraine days (MMD)

- Monthly headache hours of at least moderate pain intensity
- Monthly average duration of at least moderate pain intensity per migraine attack
- Monthly average peak migraine pain intensity
- Monthly migraine-free days
- Monthly hours of at least moderate pain intensity of triptan-treated migraine attacks

Table 5-1. Monthly Intervals for Efficacy Endpoints Derived From Daily Diary DataCollection

Study	Assessment	Monthly Interval		
Period	Timepoint	Start Date (Day) ^a	End Date (Day) ^b	
Baseline Period	Baseline	Date of device ready for entry in baseline period	Day prior to study day 1	
M-DBTP	Week 4 (Month 1)	Study Day 1	Week 4 dose date – 1	
	Week 8 (Month 2)	Week 4 dose date	Week 8 dose date – 1	
	Week 12 (Month 3)	Week 8 dose date	Week 12 dose date – 1	

^a Start Date (Day) = End date (day) of previous monthly interval + 1 if IP dose date is not available

^b End Date (Day) = Start date (day) of current monthly interval + 27 if IP dose date is not available

5.4.2 Monthly Interval for Efficacy Endpoints Derived From Episodic Diary Collection

The first qualifying triptan-treated attack during the E-DBTP will be identified within the monthly interval defined in Table 5-2:

Table 5-2. Monthly Interval for Efficacy Endpoints Derived From Episodic DiaryData

	Monthly Interval	
Study Period	Start Date (Day)	End Date (Day)
E-DBTP	Week 12 dose date	MIN (Week 12 dose date + 27, EOS date)

5.4.3 Analysis Visits for Endpoints Derived Based on Monthly Data Collection

Since the actual visit for a subject may not exactly coincide with their targeted visit date, the actual visit date is mapped to the analysis visit as in Table 5-3, Table 5-4, and Table 5-5. Any data occurred after EOS date will not be included in the analysis.

For by-visit summaries, if more than one visit with non-missing measurement (including the unscheduled visits, ie, CPEVENT = 'UNSCHED') fall within the same visit window, the following rules will be applied according to the order described below for selecting one visit per visit window for summary:

- Scheduled visit will be used regardless of the distance from the target day. Unscheduled visit will only be used when there is no measurement from scheduled visit in the visit window.
- 2. The visit closest to the target day among visits of the same type (all scheduled visits or all unscheduled visits) will be considered for analysis.
- 3. If two assessment dates are equidistant from the target date, the latter visit will be considered for analysis.

Study Period	Analysis Visit	Target Day	Visit Window (Study Day)
Baseline Period	Day 1 (Baseline)	1	Last measurement ≤ Day 1
M-DBTP	Week 4 (Month 1)	29	16 to 43
	Week 8 (Month 2)	57	44 to 71
	Week 12 (Month 3)	85	72 to 99
E-DBTP	Week 16 (Month 4)	113	100 to 127

Table 5-3. MIBS-4 Analysis Visit Windows

Table 5-4. MFIQ, MSSS and HIT-6 Analysis Visit Windows

Study Period	Analysis Visit	Target Day	Visit Window (Study Day)
Baseline Period	Day 1 (Baseline)	1	Last measurement ≤ Day 1
M-DBTP	Week 4 (Month 1)	29	16 to 43
	Week 8 (Month 2)	57	44 to 71
	Week 12 (Month 3)	85	72 to 99

Table 5-5. PGI-S, MTS and PCS Analysis Visit Windows

Study Period	Analysis Visit	Target Day	Visit Window (Study Day)
Baseline Period	Day 1 (Baseline)	1	Last measurement ≤ Day 1
M-DBTP	Week 12 (Month 3)	85	72 to 99

5.5 Subject Disposition

Randomized

Individuals are considered randomized if they have been assigned a randomization number. Randomized individuals are referred to as "subjects".

Exposed to Investigational Product

Subjects are defined as exposed if they receive at least one dose of investigational product.

Completing Investigational Product

Subjects are defined as completing investigational product if the primary reason for ending IP on End of IP eCRF is "Completed".

Completing Study

Subjects are defined as completing study if they complete the entire 16 weeks of study evaluation. It will be derived from the End of Study eCRF with "Completed" as the primary reason for ending study.

On Study

Subjects are defined as on study for specific study week if their end of study date is on or after the first day of the analysis window.

5.6 Arithmetic Calculations

Duration of Migraine

The number of years from the diagnosis date (DXDT) of migraine (migraine with aura or migraine without aura, whichever is earlier) to the date informed consent is signed.

Observed Portion	Missing Portion	Duration of Migraine (Years)
Year, Month, Day	NA	(Informed Consent Date – DXDT) / 365.25
Year, Month	Day	[Year(Informed Consent Date) – Year(DXDT)] + [Month(Informed Consent Date) – Month(DXDT)] / 12 ª
Year	Month, Day	[Year(Informed Consent Date) – Year(DXDT)] ^a

^a If it equals 0, add 1/12 years (ie, 1 month) to avoid a disease duration of 0.

Duration of IP Exposure

Minimum (Last Dose Date + 27, EOS Date) - First Dose Date + 1

Change From Baseline in Monthly Measurement

Postbaseline monthly value – Baseline, as defined in Section 5.4. If the baseline or postbaseline value is missing, the change from baseline value will be set to missing.

Change From Baseline in Mean Monthly Measurement Over Multiple Months

Change from baseline in Mean Monthly Measurement is the arithmetic mean of the monthly change from baseline values for the months considered with observed data, if there is at least one observed monthly value.

Subject Incidence of TEAEs

The subject incidence for a given event during the study is defined as the number of subjects with at least one reported occurrence of the event divided by the number of subjects who received at least one dose of investigational product. For subjects with multiple occurrences of the same event, the event will only be counted once per subject.

5.7 Disease Characteristics

Treatment Failure of Prior Migraine Preventive Medications

Treatment failure of prior migraine preventive medications is determined by "Reason for Stopping" as "Lack of efficacy" or "Adverse **event**" or "Intolerance" on the Prior Migraine Prophylactic Medication eCRF.

6. Analysis Sets

6.1 Full Analysis Set

The full analysis set consists of all subjects who were randomized in the study. Analysis of disposition, demographic and baseline characteristics, important protocol deviations, and protocol deviations related to COVID-19 control measures will utilize this analysis set.

6.2 M-DBTP Efficacy Analyses Set

The respective efficacy analysis set for each efficacy endpoint consists of a subset of subjects from full analysis set who receive at least 1 dose of investigational product and have **observed monthly hours of at least moderate headache pain intensity at baseline and at least 1 measurement during M-DBTP**. Subjects will be analyzed according to their randomized treatment, regardless of treatment received. Primary analysis of the efficacy endpoints during M-DBTP will utilize this efficacy analysis set.

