- 109 Must be the same migraine type as the initial screening period (ie, if a subject meets HFEM criteria in the 3 months prior to screening, then the subject must meet HFEM criteria during baseline).
- 110 Must have ≥ 4 migraine attacks of at least moderate severity during the baseline period.
- 111 Demonstrated at least 80% compliance with the daily eDiary during the baseline period.
- 112 Subject must treat qualifying migraine attacks with the same oral triptan as used during run-in period using 1 of the specified 4 oral triptans from inclusion criteria 107.

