9.3.1.2 Efficacy Analysis Set

The respective efficacy analysis set consists of a subset of subjects from full analysis set who receive at least 1 dose of investigational product and have a baseline value and at least 1 post baseline value for the endpoint of interest. Subjects will be analyzed according to their randomized treatment, regardless of the treatment received. Primary analysis of the efficacy endpoints will utilize the respective efficacy analysis set.

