• ≥ 14 days	Prorate to 28-day equivalent without rounding Sum of hours of headaches with at least moderate pain intensity *28/number of (diary days or days with headache pain intensity) within each monthly interval
• < 14 days	Set to missing

Monthly Hours of at Least Moderate Headache Pain Intensity of Qualifying Oral Triptan Treated Migraine Attacks

Number of Diary Days in a Monthly Interval	Monthly Hours of at Least Moderate Headache Pain Intensity of Qualifying Oral Triptan Treated Migraine Attacks
• ≥14 days	Prorate to 28-day equivalent without rounding Sum of hours of at least moderate pain intensity of qualifying oral triptan treated migraine attacks *28/number of (diary days or migraine days) within each monthly interval
• < 14 days	Set to missing

Monthly Average Duration of at Least Moderate Pain Intensity in Migraine Attacks

Number of Diary Days in a Monthly Interval	Monthly Average Duration of at Least Moderate Pain Intensity in Migraine Attacks
• ≥14 days	Sum of all the reported duration with at least moderate headache pain intensity within an attack divided by number of attacks in each month If there is no migraine during the monthly interval, then the monthly average duration will be set to 0.
• < 14 days	Set to missing

Monthly Average Duration of at Least Moderate Pain Intensity in Qualifying Oral Triptan Treated Migraine Attacks

Number of Diary Days in a Monthly Interval	Monthly Average Duration of at Least Moderate Pain Intensity in Qualifying Oral Triptan Treated Migraine Attacks	
• ≥ 14 days	Sum of all the reported duration with at least moderate headache pain intensity within a qualifying oral triptan-treated attack divided by number of qualifying oral triptan-treated attacks in each month;	
	If there is no migraine during the monthly interval, then the monthly average duration will be set to 0.	
• < 14 days	Set to missing	

Monthly Average Peak Migraine Pain Intensity

Number of Diary Days in a Monthly Interval	Monthly Average Peak Migraine Pain Intensity
• ≥14 days	Sum of observed highest pain intensity scores (NRS) per migraine day divided by total number of migraine days with at least one measure of NRS; If there is no migraine day with NRS during the monthly interval, then the monthly average peak migraine pain intensity will be set to 0.
● <14 days	Set to missing

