Worst or peak severity collected on the most bothersome symptom according to 4 levels (none, mild, moderate or severe)

Achievement of freedom from the most bothersome symptom at timed assessment post-triptan dose

Symptom severity = none at the specific timed assessment (eg, 30 minutes, 60 minutes or 2 hours post-triptan dose).

Achievement of relief from the most bothersome symptom at timed assessment post-triptan dose

Reduction in symptom severity by at least one level down (eg, from severe to moderate, mild to none) at the specific timed assessment (eg, 30 minutes, 60 minutes or 2 hours post-triptan dose).

5.1.3 Efficacy Endpoints Based on Monthly Data Collection Migraine Functional Impact Questionnaire (MFIQ)

The MFIQ version 2.0 is a self-administered 26-item instrument measuring the impact of migraine on broader functioning including 4 domains: Impact on Physical Functioning (5 items), Impact on Usual Activities (10 items), Impact on Social Functioning (5 items), and Impact on Emotional Functioning (5 items). In addition, there is 1 stand-alone global item assessing the overall impact on usual activities. Subjects respond to items using a 5-point scale assigned scores from 1 to 5, with 5 representing the greatest burden. Each domain score will be calculated as the sum of the item responses and the sum will be rescaled to a 0 to 100 scale, with higher scores representing greater burden. The recall period is the past 7 days and will be collected monthly at day 1, weeks 4, 8 and 12.

Migraine Symptom Severity Scale (MSSS)

The MSSS is a 7-item questionnaire that assesses frequency of pain and other symptoms associated with migraines. Responses are as follows: "never", "rarely", "less than half the time", "half the time or more", and "all or nearly all of the time". The responses are given a value from 0 to 3: Never = 0, Rarely = 1, Less Than Half the Time = 2, Half the Time or More = 3, and All or Nearly All of the Time = 3. The MSSS score is the sum of the responses to the 7 items with a range from 0 to 21. MSSS will be collected monthly at day 1, weeks 4, 8 and 12.

Most Troublesome Symptom (MTS)

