9.5 Efficacy Analyses

The primary and secondary efficacy analyses will utilize the M-DBTP EAS and the exploratory efficacy analyses will utilize the E-DBTP EAS. Subjects will be analyzed according to their randomized treatment group regardless of the actual treatment received during the study.

Detailed efficacy analysis methods and covariates included in the models are summarized in the table below.

Endpoint	Primary Summary and Analysis Method
Change from baseline in mean monthly hours of at least moderate headache pain intensity over months 1, 2, and 3	 Summary statistics by visit using observed data at each visit and the calculated mean monthly hours of headache pain over months 1, 2, and 3
	2. Least squares means from a linear mixed effect model including treatment group, scheduled visit, interaction of treatment and scheduled visit and baseline value using observed data
	 Estimate treatment difference (AMG 334 – Placebo) from the model in #2.

Table 9-1. Primary Efficacy Endpoint Summary Table

Table 9-2. Secondary Efficacy Endpoint Summary Table

Т

Endpoint	Primary Summary and Analysis Method
Change from baseline in mean monthly function as measured by the Migraine Functional Impact Questionnaire (MFIQ) over months	 Summary statistics by visit using observed data at each visit, and the calculated mean monthly values over months 1, 2 and 3
1, 2, and 3; Change from baseline in mean	 Least squares means from a linear mixed effect model including treatment group, scheduled visit, interaction of treatment and scheduled visit and baseline value using observed data
monthly average duration of at least moderate pain intensity in migraine attack s over months 1, 2, and 3;	 Estimate treatment difference (AMG 334 – Placebo) from the model in #2
Change from baseline in mean monthly peak migraine pain intensity as assessed by the 11-point Numeric Rating Scale (NRS) over months 1, 2, and 3	

Endpoint	Primary Summary and Analysis Method
Change from baseline in mean MMD over months 1, 2, and 3 ^a	 Summary statistics by visit using observed data at each visit and the calculated mean monthly migraine day over months 1, 2, and 3 Least squares means from a linear mixed effect model including treatment group, scheduled visit, interaction of treatment and scheduled visit and baseline value using observed data Estimate treatment difference (AMG 334 – Placebo) from the model in #2.

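### SAP 6.2 admits subjects to the confirmatory MFIQ analyses by observed diary headache hours, in place of the protocol's endpoint-specific rule

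*SAP*

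**What the plan says.** SAP 6.2 begins with wording that suggests one set per endpoint: "The respective efficacy analysis set for each efficacy endpoint consists of a subset of subjects from full analysis set". The condition that follows is the same for all endpoints. A subject must have received at least one dose and have "observed monthly hours of at least moderate headache pain intensity at baseline and at least 1 measurement during M-DBTP". The section closes with "Primary analysis of the efficacy endpoints during M-DBTP will utilize this efficacy analysis set".

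SAP 9.5 then allocates the sets: "The primary and secondary efficacy analyses will utilize the M-DBTP EAS and the exploratory efficacy analyses will utilize the E-DBTP EAS". The four MFIQ domain scores are secondary endpoints, so both sections place them in the M-DBTP set.

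Protocol 9.3.1.2 has a different condition. Subjects must be dosed and "have a baseline value and at least 1 post baseline value for the endpoint of interest".

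The two kinds of data are collected differently. Under SAP 5.1.1, monthly hours in an interval with fewer than 14 diary days are "Set to missing". For MFIQ, SAP 5.1.3 states: "The recall period is the past 7 days and will be collected monthly at day 1, weeks 4, 8 and 12". MFIQ scoring makes no use of diary-day counts.

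SAP Section 10 declares one deviation from the protocol, the split into an M-DBTP and an E-DBTP set, with a general reference to target populations. It does not mention the diary-hours criterion. SAP 9.5.1 rules out sensitivity analyses for the primary and secondary endpoints.

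**The concern.** The MFIQ domains are step 2 of the fixed testing sequence, and steps 3 and 4 follow only if it succeeds. Under SAP 6.2 a subject's place in those tests depends on keeping a diary that is not used to score them. This is an exclusion after randomisation, on a variable other than the outcome. It can remove subjects whose MFIQ was observed at baseline and after treatment.

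The subjects at risk are mainly those who stop the diary early but still attend a visit. Protocol 8.1.5 asks for the week 12 assessments, which include MFIQ, at an early termination visit. Early stoppers are a group in whom missingness may be related to response or tolerability. If the loss differs between arms and these subjects differ in outcome, the MFIQ comparison is shifted, and no planned analysis would show it.

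A second problem is that the sentence can be read in two ways. Two programmers could build different confirmatory populations from it.

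**Working it through.** **Who is excluded, on each reading**

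| Condition | Protocol 9.3.1.2, for MFIQ | SAP 6.2, natural reading | SAP 6.2, looser reading |
|---|---|---|---|
| Dose | at least 1 | at least 1 | at least 1 |
| Baseline | MFIQ value | monthly hours | monthly hours |
| Post-baseline | at least 1 MFIQ value | monthly hours in at least 1 month | at least 1 value of the endpoint itself |

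- *Baseline.* Randomisation requires "Demonstrated at least 80% compliance with the daily eDiary during the baseline period". 80% of 28 days is 22.4, so about 23 days, well above 14. The baseline condition should exclude almost nobody.
- *Post-baseline, natural reading.* A subject is lost only if all three treatment months have fewer than 14 diary days. One month with 14 keeps the subject and every MFIQ score.
- *Example.* A subject has one dose, stops the diary before day 14 and attends an early termination visit about four weeks after the dose. That MFIQ falls in the week 4 window (days 16 to 43, SAP Table 5-4) and is valid. Monthly hours are missing in months 1, 2 and 3. The protocol rule includes this subject for MFIQ; the natural reading of SAP 6.2 does not.
- *Other secondaries.* Average attack duration and peak intensity need the same 14 diary days (SAP 5.1.1), so for them the two rules select essentially the same subjects. Among confirmatory endpoints the problem is confined to MFIQ.

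**The plan's own power figures**

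Inputs from SAP Table 3-1: 288 per arm with 10% dropout, so 288 × 0.9 = 259; two-sided alpha 0.05. Formula: power = Φ(|δ| / (σ√(2/n)) − 1.96).

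- Primary: 16.7 / (50 × √(2/259)) = 3.80, power 96.7% (stated 96%).
- MFIQ social: 6.9 / (20 × √(2/259)) = 3.93, power 97.5% (stated 97%).
- MFIQ usual activities: 99.4%; physical and emotional: at least 99.9% (all three stated as above 99%).

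The stated figures are reproduced.

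**Power after extra MFIQ loss** (the loss is an assumption; the documents give none)

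| Extra loss | n per arm | MFIQ social, alpha 0.05 | MFIQ social, alpha 0.0125 |
|---|---|---|---|
| 0% | 259 | 97.5% | 92.3% |
| 1% | 256 | 97.4% | 92.0% |
| 2% | 253 | 97.3% | 91.7% |
| 5% | 246 | 96.9% | 90.8% |
| 10% | 233 | 96.1% | 89.0% |

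The last column uses 0.05/4, the strictest level in the four-endpoint Hochberg step. Social has the lowest power of the four domains.

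**Shift from selective loss**

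Let a share x_E (erenumab) and x_P (placebo) of subjects with MFIQ data be dropped, and let their mean change differ by g points from that of the retained subjects in their arm. Each arm mean moves by −x·g, so the treatment difference moves by (x_P − x_E)·g.

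- 2% and 5%, g = 10: 0.03 × 10 = 0.3 points, or 3% to 4% of the assumed effects (6.9 to 11.5 points).
- 5% and 10%, g = 20: 0.05 × 20 = 1.0 point, or 9% to 14%.
- Equal loss and equal g in both arms: no shift.

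All values of x and g are assumptions. The direction of the shift depends on which arm loses more and on the sign of g.

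**Head count.** An assumed 1% to 3% of 576 is 5.8 to 17.3, so about 6 to 17 subjects.

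**The case against.** The strongest reply is that SAP 6.2 may exclude almost nobody. Its opening words speak of a separate set per endpoint, and the measurement clause does not repeat which measurement is meant. If it means a value of the endpoint analysed, only the baseline condition depends on the diary, and criterion 111 makes that nearly always met. This reading is possible, so exclusion cannot be stated as certain. It does not clear the text, because the set for a confirmatory test should not depend on which reading a programmer chooses.

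Several other points stand. MFIQ is completed on the same handheld device as the diary (Protocol 8.2.2), so some who abandon the diary will also lack MFIQ. A subject with no contact from day 16 onward has no post-baseline MFIQ in any analysis window and fails the protocol rule too. The protocol rule is itself a restriction after randomisation. The change was deliberate: the SAP's revision history records an updated definition. One common set across a testing sequence can be defended, but the SAP does not make that case for a questionnaire endpoint.

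Two stronger readings are tempting and are not supported:

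- *That the rule governs every months 1 to 3 efficacy analysis, including HIT-6, MSSS, MIBS-4, PCS and PGI-S.* SAP 6.2 says so, but these are exploratory endpoints, and SAP 9.5 sends exploratory analyses to the E-DBTP set, which requires the week 12 dose (SAP 6.3). The sections conflict, so neither set is established for them.
- *That the rule contradicts the SAP 9.1 statement on including all observed data.* That statement is about data after non-adherence to treatment. It does not define the population, and the protocol pairs it with its own restricted efficacy set.

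**Conclusion.** The point holds for the four MFIQ secondary endpoints. SAP 6.2 replaces an endpoint-specific condition with a diary condition that has no bearing on MFIQ scoring, and Section 10 neither states nor justifies the replacement. On the natural reading, a dosed subject with valid day 1 and post-baseline MFIQ but no treatment month of at least 14 diary days is excluded. On the looser reading almost no one is, and the defect is then an ambiguous confirmatory population.

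The number affected is unknown and probably small, mainly early diary stoppers who still attend a visit. At a loss of a few percent the effect on power is negligible; even an assumed 10% costs MFIQ social 1.4 points at alpha 0.05. What remains is avoidable selective exclusion, with illustrative shifts of 0.3 to 1.0 MFIQ points. Those shifts require both unequal loss between arms and a different outcome in the subjects dropped. It should be corrected because correction is nearly free, not because a large bias has been shown.

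Separately, SAP 6.2 and 9.5 disagree on the set for exploratory months 1 to 3 endpoints.

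**What to change.** In SAP 6.2, define the M-DBTP efficacy set separately for each endpoint: randomised, dosed at least once, and with a baseline value plus one or more post-baseline M-DBTP values of the endpoint being analysed. The monthly-hours condition then applies to the primary endpoint only.

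Align SAP 9.5 with this and name there the set for exploratory months 1 to 3 endpoints, so that it no longer conflicts with 6.2. Update Section 10 so that it describes whatever difference from the protocol remains. Make the change before unblinding.

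The cost is one sentence in 6.2, matching edits in 9.5 and Section 10, and one population flag per endpoint in programming. The downside is that the number analysed will differ slightly between endpoints, which the protocol definition already allows.
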